The following signs, symptoms, observations and events are frequently observed in association with sepsis and are exempted from regulatory reporting unless known to be caused by the study drug: dyspnea, chest pain, fever, hypoxemia, rapid pulse, rapid respiratory rate, dizziness, syncope, altered mental status, seizure, confusion, anxiety, generalized weakness, anorexia, nausea, abdominal pain, back pain, constipation, vomiting, pneumonia, skin infection, cancer, surgery not related to treatment of sepsis, electrocardiography abnormalities (atrial arrhythmias, right bundle branch block, and ST and T wave changes), elevated troponin level, elevated BNP or NT ProBNP level, high white blood cell count, pulmonary infiltrate, pleural effusion, cardiomegaly, need for oxygen therapy, need for vasopressor, need for blood product transfusion, need for inotropic therapy, need for mechanical ventilation, need for physical or occupational therapy.

Expected AEs associated with the study drug (Smoflipid) include: nausea, vomiting, hyperglycemia, flatulence, pyrexia, abdominal pain, increased blood triglycerides, hypertension, sepsis, dyspepsia, urinary tract infection, anemia and device related infection, headache, sweating, dizziness, flushing, rash, urticaria, erythema, in real-time which will be recorded by the research nurse and research team.

AE Management

Any AE classified as an SAE (as per above definitions) and deemed to be related to the drug infusion will result in discontinuation of the study drug after discussion with the PI. Potential expected AEs include the following:

1. Hypersensitivity reactions resulting in rash, nausea, vomiting, shortness of breath or hypoxia
2. Respiratory distress or hypoxia occurring very soon after initiation of study drug
3. Dose Escalation and Dose-Limiting Toxicities including Fat Overload, Hypertriglyceridemia, and Refeeding Complications
4. Parenteral nutrition associated liver disease or hepatitis characterized by an elevation of liver function tests or total bilirubin

For AEs that do not meet criteria of SAEs or deemed to be “not related” or “possibly related” the PI and Co-Investigators will make decisions regarding management based on the clinical scenario.

Procedures for eliciting, recording, and reporting adverse events

Specific Instructions for Recording Adverse Events

Investigators will use correct medical terminology/concepts when reporting AEs or SAEs. Avoid colloquialisms and abbreviations.

a. Diagnosis vs. Signs and Symptoms

If known at the time of reporting, a diagnosis will be reported rather than individual signs and symptoms. However, if a constellation of signs and/or symptoms cannot be medically characterized as a single diagnosis or syndrome at the time of reporting, it will be reported based upon the information that is currently available. If a diagnosis is subsequently established, it will be reported as follow-up information.

b. Deaths

All deaths that are “more likely than not” related to the study and that occur during the protocol-specified AE reporting period will be reported to the appropriate parties.

When recording a death, the event or condition that caused or contributed to the fatal outcome will be reported as the single medical concept. If the cause of death is unknown and cannot be ascertained at the time of reporting, report “Unexplained Death”.

c. Preexisting Medical Conditions

A preexisting medical condition is one that is present at the start of the study. Such conditions will be reported as medical and surgical history.

A preexisting medical condition will be re-assessed throughout the trial and reported as an AE or SAE only if the frequency, severity, or character of the condition worsens during the study. When reporting such events, it is important to convey the concept that the preexisting condition has changed by including applicable descriptors (e.g., “more frequent headaches”).

d. Hospitalizations for Medical or Surgical Procedures

Any AE that results in prolonged hospitalization will be documented and reported as an SAE. If a subject is hospitalized to undergo a medical or surgical procedure as a result of an AE, the event responsible for the procedure, not the procedure itself, will be reported as the SAE.

Hospitalizations for the following reasons do not require reporting: Prolonged hospitalization for diagnostic or elective surgical procedures for preexisting conditions, or hospitalization or prolonged hospitalization for scheduled therapy of the target disease of the study.

e. Pregnancy

Pregnant patients will be excluded from study. In women of child-bearing age who have a uterus, pregnancy can be excluded by either urine pregnancy testing or appropriate history of abstinence, contraception with reliable menstrual history.

f. Post-Study Adverse Events

The investigator will expeditiously report any SAE occurring after a subject has completed or discontinued study participation if attributed to prior LIE.

If the investigator becomes aware of the development of cancer or a congenital anomaly in a subsequently conceived offspring of a female subject who participated in the study, this will be reported as an SAE.

Data Quality Assurance and monitoring plan

Accurate, consistent, and reliable data will be ensured through the use of standard practices and procedures. The CRF will be populated in hand by an appropriately qualified study coordinator. To qualify, the coordinator must be trained in Good Clinical Practice (GCP), and listed on the IRB-approved protocol, and must have a bachelor’s degree from college and a clinical degree (e.g., coordinator, MD, or PA). Currently, our Division of Research employs 4 GCP-trained study coordinators. Study coordinators will receive a training course via teleconference. This course will present the methods for accurate completion of CRFs and expected gray-zone issues with data entry, and the coordinators will receive a guidance document for completing the CRF. Data for CRFs will derive from one of two source documents, either the study collection template, which will contain data obtained by interview by a study coordinator, or the medical record. Sites will keep certified copies of medical records relevant to the reporting period. Sites will maintain CRFs to allow a study monitor to inspect.

Safety Monitoring

The Data Safety Monitoring Plan that includes a primary physician safety monitor (not a co-investigator) who will have expertise in critical care and the study drug. The DSM plan also includes a second safety monitor (not a co-investigator) who is a clinical trialist who also has experience in critical care. The third member of the DSM plan is a biostatistician with experience in clinical trials and critical care studies and with prior DSMB experience. All DSM meetings to evaluate for safety will be coordinated by the study monitor. The primary safety monitor will review the study data and procedures after the first patient is enrolled to evaluate the case history and any adverse events. The DSM will then meet after the fourth and eighth patient are enrolled, and at completion of the Phase I study for which results will be submitted to the IRB as a miscellaneous reportable event. Once the DSM makes the decision to move the study to Phase II, that recommendation will be submitted to the IRB, and IRB approval will be required for Phase II initiation. Subsequent meetings will occur after the thirtieth, and forty fifth patients are enrolled and after study completion. The DSM will have the authority to make one of three written recommendations to the study PI after each meeting: suspend the study, continue the study without restriction, or continue the study with contingency on review of additional data regarding adverse events, adjustments to the protocol, or individual patient's clinical history. The DSM can make additional recommendations regarding safety or study conduct as indicated for the safe and successful completion of the trial.

Data Safety Monitoring Board reports for Phase I will be submitted to the IRB for review prior to the start of the Phase II portion of the project.

Statistical Analysis

The primary method of analysis will be using an unpaired t-test of change in mean lipid levels between the groups (48 hours – enrollment) and Wilcoxon ranksum test between groups for change in SOFA score (48 hours – enrollment). Normally distributed numerical data will be compared using unpaired t-test while non-normally distributed data will be compared using Wilcoxon's ranksum. Finally, categorical data will be compared using Chi squared test. For all statistical tests $P<0.05$ will be considered significant.

Review Board

This study will be reviewed by the UF Health Jacksonville IRB.

Table 1. Schedule of Events

Assay	Serum (SST)	Plasma	Screen	T0		T48	T72	7 Days	28 days
Hospital Processed Labs									
Total cholesterol			■						
Hepatic function: total bilirubin and albumin			■						
Lipid Panels				■		■	■	■	
SOFA – platelet, creatinine, total bilirubin (if SOC labs not available for SOFA calculation)				■		■		■	
Research Processed Labs and Procedures									
Lipid absorption (from stool samples)				■		■		■	

Lipid oxidation and HDL function	■			■		■		■	
Phone follow up									■

Table 2. Sequential Organ Failure Assessment Score.

SOFA Score	0	1	2	3	4
Respiratory PaO ₂ /FiO ₂ SpO ₂ /FiO ₂	>400 >302	<400 <302	<300 <221	<200 <142	<100 <67
Cardiovascular	MAP \geq 70 mm Hg	MAP \leq 70 mm Hg	Dopamine \leq 5 or ANY Dobutamine	Dopamine >5 or Norepinephrine \leq 0.1 Phenylephrine \leq 0.8	Dopamine >15 or Norepinephrine >0.1 Phenylephrine >0.8 ANY Vasopressin
Liver Function Bilirubin, mg/dL	< 1.2	1.2-1.9	2.0-5.9	6.0-11.9	> 12
Renal Creatinine, mg/dL	< 1.2	1.2-1.9	2.0-3.4	3.5-4.9	>5.0
Coagulation Platelets \times 10 _{3/mm³}	\geq 150	<150	< 100	<50	<20
Neurologic GCS	15	13-14	10-12	6-9	<6

References

Angus, D. C., Linde-Zwirble, W. T., Lidicker, J., Clermont, G., Carcillo, J., & Pinsky, M. R. (2001). Epidemiology of severe sepsis in the United States: analysis of incidence, outcome, and associated costs of care. *Critical Care Medicine*, 29(7), 1303–1310.

Boyd, J. H., Fjell, C. D., Russell, J. A., Sironis, D., Cirstea, M. S., & Walley, K. R. (2016). Increased Plasma PCSK9 Levels Are Associated with Reduced Endotoxin Clearance and the Development of Acute Organ Failures during Sepsis. *Journal of Innate Immunity*, 8(2), 211–220. <https://doi.org/10.1159/000442976>

Catapano, A. L., Pirillo, A., Bonacina, F., & Norata, G. D. (2014). HDL in innate and adaptive immunity. *Cardiovascular Research*. <https://doi.org/cvu150> [pii]

Chien, J.-Y., Jerng, J.-S., Yu, C.-J., & Yang, P.-C. (2005a). Low serum level of high-density lipoprotein cholesterol is a poor prognostic factor for severe sepsis. *Critical Care Medicine*, 33(8), 1688–1693. Retrieved from <http://www.ncbi.nlm.nih.gov/pubmed/16096442>

Chien, J.-Y., Jerng, J.-S., Yu, C.-J., & Yang, P.-C. (2005b). Low serum level of high-density lipoprotein cholesterol is a poor prognostic factor for severe sepsis. *Critical Care Medicine*, 33(8), 1688–1693. <https://doi.org/10.1097/01.CCM.0000171183.79525.6B>

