D. UF Jacksonville sepsis recruitment. UF JAX Emergency Dept. patients meeting criteria will be identified by the PI and Co-I ([name]) and the research team who will be notified via pager. Prior to approaching the patient or the LAR for consent in the study, the clinical staff will approach the patient or LAR and ask them about their interest in hearing about the study. If the patient or LAR express interest, the research team will review eligibility criteria, and will seek consent. Time block sampling will be used to enroll patients between the hours of 7am and 12am, 7 days/week.⁴⁵ The team has enrolled a mean of 5 patients per month in previous studies, including [name] K23 study.

[figure not shown]

Figure 1

4.3. Enrollment Criteria.

A. Inclusion Criteria: 1) age ≥ 18 , 2) primary diagnosis of sepsis and within 24 hours of sepsis recognition and treated with institutional sepsis algorithm, 3) SOFA score ≥ 4 with at least 2 points being new or sepsis with vasopressor dependence, 4) screening total cholesterol ≤ 100 mg/dL or HDL-C + LDL-C ≤ 70 mg/dL, Screening lipids will be billed to the study.

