4.8 Efficacy Endpoints

A. Primary Endpoints

- Delta (48h - enrollment) serum total cholesterol of 0 to 5 mg/dL

B. Secondary Endpoints

- Lipid oxidation (HDL inflammatory index)
- HDL function (cholesterol efflux capacity)
- Change in SOFA score over the first 48h and 7 days
- In-hospital mortality
- Change in cholesterol level from enrollment to 7 days

4.9 Study Procedures.

A. Randomization

Phase II of this study/trial will use an adaptive design. As the study progresses, the dose of the study drug that proves least efficacious for stabilizing cholesterol levels will be dropped. For the first 24 patients, patients will be randomized to receive one of three doses of the study drug, or no drug (active control). The first 24 patients will be randomized using the following allocations: 4:4:4:12. From the first 24 patients, we will select the two doses that have the best performance in the primary endpoint, Delta (48h - enrollment) serum total cholesterol of 0 to 5 mg/dL, among the ones that are acceptable in safety. We will also evaluate Delta SOFA score at 48 hours (organ failure score, from 48h-enrollment) as well as Delta 7 days for serum total cholesterol (7 day – enrollment) to select the two most efficacious doses. For the last 24 patients in the study, patients will be randomized to receive one of the two most efficacious doses of study drug based on results from the first 24 patients in the following manner: 6:6:12, or no drug (active control). The overall study groups will include 24

patients in the experimental arm and 24 patients in the control arm as originally designed. The study will employ a permuted blocked randomization technique. Permuted blocked randomization has several advantages in that it supports group balance at the end of the trial and it supports continuous balance during trial progression by assuring that sequential patients are distributed equally between groups. The study statistician will generate the randomization sequence that will be stored in REDCap and accessed by the study coordinators at the time of patient enrollment.

B. Blinding. Because this is a pilot study, and because the lipid emulsion appears white and will be visible to the treatment team, the study will not be blinded. Data abstractors will, however, be blinded to the treatment effect. As the treatment effects are objective measurements (lipid levels, SOFA score, etc.) the likelihood of bias is low.

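### Table 2 has no epinephrine entry and scores the kidney on creatinine alone, so dialysis, or epinephrine given in place of the listed vasopressors, can score as SOFA recovery

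*Combined protocol and SAP*

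**What the plan says.** Section 4.8 B lists as a secondary endpoint "Change in SOFA score over the first 48h and 7 days". Section 4.9 G, repeated in the Data Safety Monitoring Plan, gives the 48-hour change its own Wilcoxon rank-sum test.

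Section 4.9 A allocates the first 24 patients 4:4:4:12 to three doses and control, then carries two doses forward. Performance on the cholesterol endpoint comes first, among doses with acceptable safety. The section then adds "We will also evaluate Delta SOFA score at 48 hours", together with the 7-day cholesterol change. It gives no weights.

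Table 2 is the scoring instrument. Below the vasopressor columns, the cardiovascular row uses MAP. The 2-point cell ends with "ANY Dobutamine", the 3-point cell begins "Dopamine >5 or Norepinephrine", and the 4-point cell is "Dopamine >15 or Norepinephrine >0.1 Phenylephrine >0.8 ANY Vasopressin". The renal row is labelled "Renal Creatinine, mg/dL" and consists of creatinine bands only.

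Three other places bear on the point:

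- Section 4.3 A admits patients with "SOFA score ≥ 4 with at least 2 points being new or sepsis with vasopressor dependence". Dialysis is not among the 18 exclusions in 4.3 B.
- Table 1 schedules, at enrollment, 48 hours and day 7, "SOFA – platelet, creatinine, total bilirubin (if SOC labs not available for SOFA calculation".
- The data quality section of the monitoring plan promises coordinator training and a guidance document for completing the CRF, and names the medical record as a data source. The guidance document is not supplied.

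**The concern.** A change in organ-failure score should not fall because one form of organ support has replaced another, or because a machine is clearing the marker being measured. As written, Table 2 allows both. Dialysis lowers creatinine without renal recovery, and the renal row cannot tell the two apart. A patient whose pressure is held by epinephrine alone is scored on MAP, as if on no vasopressor, although section 4.3 A treats vasopressor dependence as sufficient for entry.

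The error can also run the other way. A patient on epinephrine alone at enrollment who is later moved to norepinephrine scores as worse.

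At stake are a secondary endpoint with its own test and one of the supporting inputs to a dose choice made on 4 patients per dose. Section 4.9 B also defends the open-label design by calling SOFA an objective measurement. That defence is weaker if each abstractor must decide how to score these cases.

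**Working it through.** **1. The plan's own figure.** The documents give no power or SD for SOFA change. The only power figure is for cholesterol (section 4.9 D): effect sizes 17/23 = 0.74 and (17 + 2)/23 = 0.83, with 24 per arm and alpha 0.05. A two-sided two-sample t-test (46 df) gives 70.8% and 80.0%, against the stated 71% and 80%. The figure reproduces. It uses no SOFA data, so this point leaves it unchanged.

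**2. Cardiovascular row of Table 2, applied literally.**

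| Course from enrollment to 48 h | Score | Change |
|---|---|---|
| Norepinephrine >0.1 replaced by epinephrine alone, MAP above 70 | 4 to 0 | −4 |
| Same, MAP below 70 | 4 to 1 | −3 |
| Norepinephrine ≤0.1 replaced by epinephrine alone, MAP above 70 | 3 to 0 | −3 |
| Same, MAP below 70 | 3 to 1 | −2 |
| MAP below 70 on no vasopressor, then epinephrine with MAP above 70 | 1 to 0 | −1 |
| Epinephrine added to norepinephrine >0.1 | 4 to 4 | 0 |
| Epinephrine added to norepinephrine ≤0.1 | 3 to 3 | 0 |

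A false improvement of 2 to 4 points therefore needs epinephrine to replace every listed agent. As the first vasopressor it gives at most −1. As an add-on it gives 0.

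**3. Renal row, applied literally.** The creatinine values are illustrative; the bands are Table 2's.

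| Creatinine before and during dialysis (mg/dL) | Score | Change |
|---|---|---|
| 5.5 to 1.8 | 4 to 1 | −3 |
| 5.5 to 3.0 | 4 to 2 | −2 |
| 4.0 to 1.8 | 3 to 1 | −2 |

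**4. Effect on a group mean.** One patient misscored by k points moves the mean of n patients by k/n.

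| k | n = 4 (one dose at selection) | n = 24 (full arm) |
|---|---|---|
| 2 | 2/4 = 0.50 | 2/24 = 0.08 |
| 3 | 3/4 = 0.75 | 3/24 = 0.13 |
| 4 | 4/4 = 1.00 | 4/24 = 0.17 |

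Four points is the whole range of one organ row, so 1.00 and 0.17 are the limits for one misscored row in one patient.

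**5. Illustration for dose selection.** Two assumptions are not in the documents: three equally effective doses are ranked on mean 48-hour SOFA change alone, and the SD of that change is 2 to 4 points. In a simulation of 200,000 runs with 4 patients per dose, each dose has a 33% chance of being dropped. If one patient in a dose group is misscored in the favourable direction, that group's chance becomes:

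| Misscore | SD 2 | SD 3 | SD 4 |
|---|---|---|---|
| −2 | 21% | 24% | 27% |
| −4 | 11% | 17% | 21% |

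The plan does not rank on SOFA alone, so these figures overstate its role. They show how sensitive a 4-patient mean is, not what would happen in this trial.

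**The case against.** The strongest reply has five parts.

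- **Escalation.** A reader might infer that any escalation to epinephrine scores as recovery. Table 2 does not support that: added to a listed agent, epinephrine changes nothing. The large false drops require substitution, which is not plainly escalation. This stands and limits the epinephrine half of the point. It does not touch the dialysis half.
- **Data capture.** A reader might infer from Table 1 that only platelets, creatinine and bilirubin are collected for SOFA. That row lists back-up laboratory tests for when routine results are missing. MAP, vasopressors, GCS and oxygenation are not in it either, yet the score needs them. So Table 1 does not show what is abstracted. The CRF guidance may cover these cases, but it cannot be checked, and a rule that decides an endpoint belongs in the protocol.
- **Dose selection.** A reader might infer that SOFA decides which doses continue. Section 4.9 A puts cholesterol first and requires acceptable safety; SOFA change is also evaluated, with no weight and no stated use of means. This stands.
- **Final test.** A rank-sum test limits the leverage of one patient, and the same table applies in every arm, so false credit to a dose needs an imbalance in dialysis or vasopressor substitution. This stands for the 24-versus-24 comparison. With 4 patients per dose, chance imbalance is easy.
- **Frequency.** The documents give no rate of epinephrine or dialysis use, and 4.3 B excludes refractory shock. The expected bias cannot be estimated.

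**Conclusion.** The point holds within those limits. Two gaps in a stated scoring rule produce wrong scores when the rule is followed: dialysis can score as renal recovery, and epinephrine substituted for the listed vasopressors can score as cardiovascular recovery. Nothing in the supplied text overrides Table 2.

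For one misscored patient the effect is 0.5 to 1.0 points on a 4-patient dose mean and at most 0.17 on a 24-patient arm mean. The conclusion rests on a literal reading of Table 2, on misscores of 2 to 4 points in one organ row, and on at least one such patient being enrolled. It does not extend to the primary endpoint or the sample size, and it does not establish that the SOFA comparison is biased in a particular direction. The table should be amended because the correction is cheap and the scores feed a decision made on very small groups.

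**What to change.** In Table 2, score epinephrine as a vasopressor in the 3 and 4 columns alongside norepinephrine, and write down the boundary between the two columns. For the outcome scores, assign the highest renal category while the patient is on renal replacement therapy, so that dialysis cannot score as improvement. Take both items from the chart at T0, T48 and day 7, and apply the same rule in all arms. This concerns outcome scoring only and changes no treatment.

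The cost is two table edits and one added CRF item for renal replacement. There are two consequences to accept and state:

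- Patients on chronic dialysis will show no renal change.
- If the same table is used at screening, a dialysis patient reaches a SOFA of 4 from the kidney alone. The protocol should say that the existing requirement for at least 2 new points still applies at entry.
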